## 6. STUDY PROCEDURES

### 6.1. Study Schematic

The intervals and schedule of events are provided in Table 1.

	Retrospective Data Collection 				Prospective Data Collection 
	Screening and Enrollment	Pre-operative	Operative / Discharge	Follow-up	
Informed Consent	✓ 				
Inclusion/Exclusion	✓				
Demographics/ Medical History		✓			
Operative and Discharge Data Collection			✓		
Implant Status 				✓	✓
Knee Society Score (KSS)		✓		✓	✓
VR-12		✓		✓	✓
Radiographic Assessment		✓	✓	✓	✓
Adverse Event Assessment			✓	✓	✓
End of Study/Exit				✓*	✓

Given the retrospective-prospective study design, data will be collected to the extent it is available.

Visit may occur in an office or remotely. If completed remotely (e.g. telephone call, mailing of subject questionnaires and/or any other means), secondary endpoint data will be collected to the extent possible.

Informed consent/waiver of informed consent from the IRB/EC must be obtained prior to retrospective and prospective data collection.

Subjects who have undergone a revision procedure of the study knee will be considered terminated from the study from the date of the revision. Study related data will not be collected following the date of the revision.

\*if applicable

### 6.2. Retrospective Data Collection

- Verify subject meets inclusion/exclusion criteria
- Obtain Informed Consent, as required by the IRB/EC, on an IRB/EC approved ICF or a waiver of informed consent
- Assign a Subject ID
- Collect the following retrospective data, to the extent it is available in the subject's medical records, per CRF completion guidelines:
  - Demographic and medical history information
  - Operative and Discharge data
  - Implant Status

- KSS – pre-operative and any available postoperative follow-up
- VR-12 – pre-operative and any available postoperative follow-up
- Pre-Operative anterior/posterior and lateral radiographic assessments:
  - Radiographic findings
  - Osteolysis
- Post-Operative anterior/posterior and lateral radiographic assessments that are available:
  - Radiographic findings
  - Component orientation
  - Radiolucencies
  - Migration
  - Osteolysis
  - Stress shielding
  - Subsidence
- Revision CRF, if applicable
- End of Study CRF, if applicable
- Study Device and Procedure-Related Adverse Events

### **6.3. Prospective Data Collection: 2-Year (-3 months) or Greater Postoperative Follow-up**

Collect the following prospective data for subjects who have not retrospectively completed a 2-year (-3months) or greater postoperative visit and consent to participate in the prospective phase of the study:

- Implant Status
- KSS
- VR-12
- Anterior/Posterior and lateral radiographs and assessments:
  - Radiographic findings
  - Component orientation
  - Radiolucencies
  - Migration
  - Osteolysis
  - Stress shielding
  - Subsidence
- Revision CRF, if applicable
- End of Study CRF
- Study Device and Procedure-Related Adverse Events

The prospective follow-up visit may occur in an office or remotely. If completed remotely (e.g. telephone call, mailing of subject questionnaires and/or any other means), secondary endpoint data will be collected to the extent possible.

If the subject already completed the 2-year visit at the time of enrollment, 2-year visit data will be collected retrospectively as defined in section 6.2.

## 7. SUBJECT COMPLETION AND DISPOSITION

### 7.1. Conditions for Study Termination

All reasonable efforts should be made to collect 2-year postoperative data on all subjects enrolled in this study. There are multiple reasons a subject may be terminated from the study. For each case, information will be obtained on the End of Study CRF, detailing circumstances leading to the withdrawal.

#### A. Voluntary Withdrawal

Study participation is voluntary and subjects may withdraw from the study without giving reason for doing so.

#### B. Lost to Follow-Up

During the course of this study, it may not be possible to locate a subject for informed consent and participation prospectively. Study personnel must make a reasonable effort to contact the subject and document the contact attempts according to the site's policies prior to declaring a subject to be lost to follow-up. Copies of all attempts to reach the subjects by regular mail, email and/or any other means should be documented in the subject's medical record.

#### C. Study Termination by Investigator/Sponsor

The Investigator **should** withdraw subjects from the study:

- if the study knee was revised during the follow-up phase of the study
- if the Investigator or the Sponsor stops the study for any reason

#### D. Pregnancy

In the unlikely event that a subject becomes pregnant from the time point of signing the Informed Consent until the end of the study, study procedures that are contraindicated during pregnancy and/or lactation (e.g. x-rays) will not be obtained. However, the subject will continue to be followed and information will be collected regarding the outcome of the pregnancy.

#### E. Study Site Discontinuation

A specific study site in this multicenter study may also warrant termination under the following conditions:

- non-compliance to GCP or protocol
- failure to enroll subjects
- major protocol deviations
- inaccurate or incomplete data
- unsafe or unethical practices
- safety or performance considerations
- investigator involuntarily discontinues participation in study

#### F. Revisions

Subjects who have undergone a revision procedure of the study knee will be considered terminated from the study from the date of the revision. Study-related data will not be collected following the date of the revision. The appropriate CRFs will be completed for these subjects to document the details of study termination and revision.

## **8. SAFETY REPORTING**

Adverse Events (AE) related to the study device (Navio), the unicondylar implant, or procedure including Adverse Device Effects (ADE), Serious Adverse Device Effects (SADE), Unanticipated Serious Adverse Device Effect (USADE), and Device Deficiencies (DevD) occurring from the time of the study procedure until revision or study completion must be recorded on the appropriate CRF and reported. If the event is known to have been previously reported to Smith & Nephew, this must be noted on the CRF. After consent, in addition to all events related to Navio, the unicondylar implant or the procedure, all serious adverse events (SAE), regardless of causality, must be recorded on the appropriate CRF and reported to sponsor and IRB if necessary. Events leading to a revision should be reported at all times regardless of causality.

Adverse Device Effects (ADE) occurring after study completion will be handled as product complaints reportable by the Sponsor and will not be entered into the study database.

### **8.1. Definitions for Safety Reporting**

#### **A. Adverse Event**

An AE is any untoward medical occurrence, unintended disease or injury, or untoward clinical signs (including abnormal laboratory findings) in subjects, users, or other persons whether or not related to the investigational medical device (10).

For the purpose of this study, this definition includes:

- events related to either Navio or the unicondylar implant
- events related to the procedures involved
- during the prospective data collection period, a worsening of any conditions previously recorded as part of the medical history assessment that meets serious adverse event criteria

#### **B. Serious Adverse Event (SAE)**

An SAE is an AE that (10):

- led to death,
- led to serious deterioration in the health of the subject, that either resulted in:
  - 1) a life-threatening illness or injury, or
  - 2) a permanent impairment of a body structure or a body function, or
  - 3) in-patient or prolonged hospitalization, or
  - 4) medical or surgical intervention to prevent life-threatening illness or injury or permanent impairment to a body structure or a body function
- led to fetal distress, fetal death or a congenital abnormality or birth defect

Planned hospitalization for a pre-existing condition, or the study procedure, without serious deterioration in health, is not considered a serious adverse event.

#### **C. Adverse Device Effect (ADE)**

An ADE is an AE related to the use of an investigational medical device (10).

This definition includes:

- AEs resulting from insufficient or inadequate instructions for use, deployment, implantation, installation, or operation, or any malfunction of the investigational medical device
- Any event resulting from use error or from intentional misuse of the investigational medical device.
- For the purposes of this study, any event related to a Smith & Nephew unicondylar implant will be classified as an adverse device event

#### **D. Serious Adverse Device Effect (SADE)**

An SADE is an ADE that has resulted in any of the consequences characteristic of an SAE (10).

#### **E. Unanticipated Serious Adverse Device Effect (USADE)**

An USADE is an SADE which by its nature, incidence, severity or outcome has not been identified in the current version of the risk analysis report or the clinical investigation plan (10, 11).

#### **F. Device Deficiency (DevD)**

A DevD is an inadequacy of a medical device with respect to its identity, quality, durability, reliability, safety, or performance. DevD include malfunctions, use errors, and inadequate labeling.

For this study, DevD should be reported when they concern any component of the Navio system as well as its packaging and tools that need to be used during surgery according to the User Manual.

#### **G. Revisions**

A specially designed Revision CRF will be used in addition to the AE CRF, to document in detail revisions of any study knee. Please note that at all phases of the study, all revisions should be reported, regardless of whether or not it is related to Navio, the unicondylar knee or the study procedure.

#### **8.2. Safety: Investigator's Responsibilities**

##### Reporting of adverse events during the retrospective data collection portion of the study:

Investigators are responsible for documenting ADE, SADE, U(S)ADE and DevD identified during the medical record review. This includes events related to the study device (Navio), the unicondylar implant, or procedure. Investigators will record ADE, SADE, U(S)ADE and observed DevD, together with an assessment in the subject's source data. Investigators are responsible for documenting ADE, SADE, U(S)ADE and DevD on the appropriate CRF and submitting them to the Sponsor according to the timelines described.

##### Reporting of adverse events during the prospective data collection portion of the study:

At each prospective contact with the subject, the Investigator must seek information on previous events and current events that could be deemed serious by specific questioning and, as appropriate, by assessment of the subject. All study device (Navio), unicondylar implant, and procedure related adverse events and all serious adverse events (SAE) regardless of causality, must be recorded on the appropriate CRF and reported to sponsor and IRB. Unresolved AE should be followed by the Investigator until the events are resolved or through to the end of the study, whichever occurs first. Unresolved AEs at the end of the subject's participation should be monitored by the Investigator as part of the site's normal standard of care.

All events must be recorded in standard English medical terminology.

The Investigator will categorize AE as mild, moderate or severe based on the following definitions:

- Mild: the subject is aware of the sign or symptom, but finds it easily tolerated. The event is of little concern to the subject and/or little clinical significance. The event is not expected to have any effect on the subject's overall health or well-being.
- Moderate: the subject has discomfort enough to cause interference with or change in usual activities. The event is of some concern to the subject's health or wellbeing and may require medical intervention and/or close follow-up.
- Severe: the adverse event interferes considerably with the subject's usual activities. The event is of definite concern to the subject and/or poses a substantial risk to the subject's health or wellbeing. The event is likely to require medical intervention and/or close follow-up and may be incapacitating or life threatening. Hospitalization and treatment may be required.

The Investigator is responsible for describing the relationship of the AE to the study device/procedure based on the following definitions:

- Unrelated: the event is clearly not related to the study device or procedure
- Possible: the event may or may not be related to the study device or procedure. A relationship cannot be ruled out.
- Definite: the event is clearly related to the study device or procedure.

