**Protocol Synopsis:**

Title of Study:	A Retrospective Study of the Navio ◊ Robotic-assisted Surgical System
Study Type:	Post-market
Study Device:	Navio ◊ Robotic-assisted Surgical System
Indications	Navio System-assisted Unicondylar Knee Replacements (UKR) are indicated for restoring either compartment of a knee that has been affected by: 
 
• Non-inflammatory degenerative joint disease including osteoarthritis, traumatic arthritis, or avascular necrosis
 
• Correction of functional deformity
 
• Treatment of fractures that are unmanageable using other techniques
 

Study design:	A retrospective, multi-center, cohort study with prospective follow-up and comparison to historical control
Primary Endpoint:	Navio System assisted Unicondylar Knee Replacement (UKR) revision rate 2 years postoperative
Secondary Endpoints:	Given the retrospective-prospective study design, secondary endpoint data will be collected to the extent that it is available and will include: 
 
• Change in Knee Society Score (KSS) from baseline to 2 years (-3months) or greater postoperative
 
• Change in VR12 from baseline to 2 years (-3months) or greater postoperative
 
• Anterior/Posterior and lateral radiographic assessments
 

Safety Assessment:	Study device and procedure-related adverse events (AE) incidence and frequency
Length of Study:	Up to 1 year: includes enrollment phase and collection of a minimum of 2-year postoperative follow-up data
Study Visits:	Retrospective pre-operative, operative and any available postoperative follow-up; Prospective 2-year or greater postoperative follow-up
Number of Sites:	Up to 10 sites in the United States and Europe
Sample Size:	One hundred twenty-eight (128) subjects, including 10% inflation to allow for attrition
Inclusion Criteria:	
 
1. Male or female subjects ≥18 years old (at the time of surgery) who have undergone Navio System-assisted UKR prior to IRB/EC site approval. This includes UKR procedures with all Unicondylar Knee cemented implant designs.
 
2. Subject had a primary diagnosis of unicompartmental, non-inflammatory degenerative joint disease including osteoarthritis, traumatic arthritis, or avascular necrosis, required correction of functional deformity, or required treatment of fractures that were unmanageable using other techniques.
 

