5.4 Safety Endpoints

Safety endpoints are as follows:

- Incidence of AEs,
- Incidence of AEs by severity,
- Incidence of AEs by relationship to knee implant (study device),
- Incidence of AEs by relationship to NAVIO System,
- Incidence of AEs that led to discontinuation,
- Incidence of AEs by outcome,
- Incidence of serious adverse events (SAEs),
- Incidence of adverse device effects (ADE),
- Incidence of serious adverse device effects (SADEs),
- Incidence of unanticipated adverse device effects (UADEs),
- AEs of special interest,
- Listing of revisions and details of components removed during revision.

6. Statistical Considerations

CONFIDENTIAL AND PROPRIETARY

This document contains information that is confidential and proprietary to Smith & Nephew PLC and Smith & Nephew, Inc. and is intended for use only by Smith & Nephew and its manufacturer. It shall not be reproduced or copied in whole or in part, nor shall the contents be disclosed by any means without prior written permission from Smith & Nephew, nor shall anyone make any use of it that is contrary to the expressed or implied wishes of Smith & Nephew.

Statistical Analysis Plan	 smith&nephew
A Retrospective Study of the NAVIO Robotic-assisted Surgical System	Number: 16-NPFS-11
	Version: Final 1.0, Jan 29, 2018
	Page: 12 of 25

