7.13 Analysis of Safety Endpoints

CONFIDENTIAL AND PROPRIETARY

This document contains information that is confidential and proprietary to Smith & Nephew PLC and Smith & Nephew, Inc. and is intended for use only by Smith & Nephew and its manufacturer. It shall not be reproduced or copied in whole or in part, nor shall the contents be disclosed by any means without prior written permission from Smith & Nephew, nor shall anyone make any use of it that is contrary to the expressed or implied wishes of Smith & Nephew.

Statistical Analysis Plan	 smith&nephew
A Retrospective Study of the NAVIO Robotic-assisted Surgical System	Number: 16-NPFS-11
	Version: Final 1.0, Jan 29, 2018
	Page: 23 of 25

- An overall summary AE table that would summarize as number (n) and percentages (%), the overall incidence according to subjects with at least one AE; subjects with at least one AE by worst severity (mild, moderate, or severe); subjects with at least one AE by worst outcome; subjects with an AE that led to study discontinuation; subjects with at least one AE by worst relatedness to investigational device; subjects with AEs by worst relationship to the NAVIO device; SAEs; ADEs; SADEs; UADEs and; AEs of special interest would be summarized. A Smith and Nephew Adverse Event Monitoring Board (AEMB) may be convened to review the list of and subsequently classify AEs into special interest AEs for additional AE summaries.
- Tables that summarize the incidence of AEs (each based on criteria previously specified in the overall summary table) would be generated. Each table would include the numbers (n) and percentages (%) of subjects with each AE as well as the cumulative events/episodes per AE.

All summaries and listings for the safety endpoints would use the safety population as the analysis population.

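### The questioning instruction in protocol 8.2 is narrower than the recording rule and the safety endpoint, so non-serious related AEs may be under-ascertained at the prospective contact

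*Protocol*

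**What the plan says.** The instruction on finding events at prospective contacts is in protocol 8.2: "the Investigator must seek information on previous events and current events that could be deemed serious by specific questioning". The same sentence adds a second route, "as appropriate, by assessment of the subject".

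The next sentence sets what must be recorded, and it is wider: "All study device (Navio), unicondylar implant, and procedure related adverse events and all serious adverse events (SAE) regardless of causality, must be recorded". The opening of section 8 gives the same scope for related events, for those "occurring from the time of the study procedure until revision or study completion must be recorded on the appropriate CRF and reported". Section 6.3 lists device- and procedure-related AEs among the items to collect at the prospective visit, with no seriousness limit. Table 1 ticks AE assessment in the prospective column.

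The endpoint follows the wider scope. The synopsis gives the safety assessment as "Study device and procedure-related adverse events (AE) incidence and frequency". SAP 5.4 lists "Incidence of AEs by severity", and SAP 7.13 tabulates "subjects with at least one AE by worst severity (mild, moderate, or severe"). Protocol 9.4 puts 95% confidence intervals on the AE rates.

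For the retrospective portion, 8.2 relies on events "identified during the medical record review".

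**The concern.** A recording rule applies to events the investigator already knows about. The questioning instruction does much to decide which events become known. In 8.2 the instruction to ask is tied to potential seriousness, while the duty to record and the endpoint are not. A site could follow the questioning sentence exactly, record everything it learned, and still have an incomplete count of non-serious related AEs.

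Serious events would then be actively sought, while some non-serious ones would depend on the chart, on the subject volunteering them or on an assessment. That is differential ascertainment within one safety table. The intervals planned in protocol 9.4 describe sampling error and would not reveal it. The study's stated objective is 2-year safety and effectiveness, so a low rate of non-serious related AEs would be read as a finding about the device when part of it could come from how subjects were asked.

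**Working it through.** The documents state no figure for this point, so the check is a comparison of wording.

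**Step 1: scope of each instruction (all protocol unless marked).**

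- Questioning (8.2, prospective): previous events and current events, with a seriousness qualifier.
- Assessment (8.2, same sentence): where appropriate.
- Recording (8.2, next sentence; section 8): all related AEs, plus SAEs of any cause in the prospective portion.
- Visit item (6.3, Table 1): related AEs, no seriousness limit.
- Endpoint (synopsis; SAP 5.4 and 7.13): related AEs in the synopsis, AEs by severity in the SAP, with no seriousness limit in either.

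Only the questioning clause carries the qualifier.

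**Step 2: the two ways to parse the questioning clause.** The qualifier can attach to current events alone or to both previous and current events.

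| Related event | Qualifier on current only | Qualifier on both |
|---|---|---|
| Previous, potentially serious | asked | asked |
| Previous, non-serious | asked | not asked |
| Current, potentially serious | asked | asked |
| Current, non-serious | not asked | not asked |

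The last row is the same under both parsings. The second row depends on the parsing, and the text does not settle it.

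**Step 3: whether another route closes the gap.** Assessment of the subject could find some of these events at an office visit. Section 6.3 also allows the visit to be done remotely, for example by telephone or mailed questionnaire. Assessment is then limited and questioning is the main tool. The visit list in 6.3 names the data item but does not say how to elicit it.

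**Step 4: which subjects are reached.** Under 6.3 the prospective visit is for subjects with no 2-year (-3 months) or later visit on record who consent to the prospective phase. Section 5.2 lets subjects consent to the retrospective phase only. Everyone else contributes AEs through record review, which the questioning sentence does not touch.

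**Step 5: which events are exposed.** Section 8.1 B defines seriousness by consequence (death, hospitalization, permanent impairment and so on). Section 8.2 grades severity by tolerability and interference with activities. The scales differ: an event graded moderate can be serious, and one graded severe can be non-serious. The exposed group is non-serious related events, whatever their severity grade.

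**Step 6: what would be needed for a size.** Let N be the safety population and m the number with a prospective contact. Let p be the true share with a non-serious related AE, taken as equal in both groups for simplicity. Let c be the capture share at contacts under the present text and c* the share under full questioning. The shortfall due to this sentence is

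p × (m / N) × (c* − c).

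Asking about more events should not lower capture, so c* ≥ c and the shortfall is zero or positive. Enrollment is planned at 128, but the documents give none of p, m, c or c*. The direction follows from the text and the size does not.

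**Step 7: the primary endpoint.** Section 8.1 G requires all revisions to be reported at all phases, whether or not related. The gap does not reach the revision analysis.

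**The case against.** The strongest reply is that this is one loosely drafted clause among instructions that agree with the endpoint. Section 8, section 6.3, Table 1 and the very next sentence of 8.2 all call for related AEs without a seriousness limit, and assessment of the subject is a stated route. A sensible investigator would ask about any problem with the knee. If the qualifier attaches only to current events, most of the history since surgery is open to questioning and the gap is confined to non-serious events still present at the contact. The AE CRF (version 3.0, per SAP section 2) is not among the documents, and its prompt may already ask the wider question. The AE tables are descriptive, with no hypothesis test.

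Much of this stands. It limits the point to a risk in one clause and keeps it away from the primary analysis. It does not remove the mismatch, because no sentence tells the investigator to ask about a current non-serious related event.

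A reader might go further and infer that mild and moderate related events are in fact under-counted, or put a percentage on the loss across all 128 subjects. The documents support neither. They show a risk of incomplete ascertainment and not an observed deficit. The exposed category is non-serious events, which is not the same as mild and moderate ones. Any percentage would rest wholly on assumed event and capture rates, and applying it to everyone enrolled would charge the limits of chart review to a sentence that governs only prospective contacts.

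**Conclusion.** The mismatch is real and narrow. Among subjects with a prospective contact, current non-serious AEs related to the Navio system, the implant or the procedure are not actively asked about on either parsing. On the broader parsing, previous ones are not asked about either. Their incidence is therefore liable to be under-ascertained relative to serious events. The conclusion assumes that sites follow the questioning sentence as written and that the CRF prompt does not already widen it. The direction is downward, the size cannot be derived from the documents, and the revision endpoint is unaffected. The change is worth making mainly because it is cheap and brings the questioning into line with the protocol's own recording rule.

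**What to change.** Reword the sentence in protocol 8.2 so that, at each prospective contact, in the office or remote, the investigator asks about any event since surgery related to the Navio system, the implant or the procedure, serious or not, and about any other event that could be serious. Check that the AE CRF prompt matches, and amend it if it does not.

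In the study report, state that rates of non-serious related AEs are minimum estimates where they come from record review only or from contacts made under the present text of 8.2. A sentence with the AE tables is enough. Splitting the rows by how subjects were questioned would give sparse cells in a study of this size.

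The cost is one protocol sentence, a CRF check and one statement in the report, with no change to visits, sample size or the primary analysis. The downside is a few more minor AEs to record and a somewhat higher reported AE incidence. Subjects with record review only gain nothing from the rewording, which is why the statement in the report is still needed.
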